5.1.1 Study Summaries

Study summaries will be generated every 6 months and forwarded to the FDA and Merck, which is providing study support, in addition to the annual reporting requirements outlined in section [7.4.2](#).

5.2 RESPONSE CRITERIA

The primary focus of this clinical study is immunogenicity as measured by development of and change in antibody titers to the four HPV types within the quadrivalent HPV vaccine. HPV-specific antibody titers will be measured at baseline and s/p receipt of 1, 2 and 3 doses of vaccine, in addition to serial, longitudinal monitoring of HPV titers every 6 months following completion of the vaccination series for a total of 4 years to assess antibody titer decay and duration of immunogenicity.

The only clinical outcomes that will be monitored for response are for safety criteria, as this study is not statistically powered to assess vaccine efficacy even on a preliminary level in the currently defined study cohort populations. Safety will be monitored through the use of Vaccination Report Card (VRC) Surveillance for Adverse Vaccine Experiences to assess local injection site and systemic reactions to vaccination, in addition to monitoring of laboratory values. In HIV-infected study subjects, this safety assessment also includes virologic parameters to ensure that HPV VLP vaccination is not associated with upregulation of viral replication and increased HIV-1 RNA levels.

Research assessments that will be evaluated in a descriptive observational manner include:

- Cross-sectional characterization of HPV DNA positivity by oral/buccal and anogenital swabs at baseline in the study cohort populations.
- Longitudinal changes following vaccination in:
 - lymphocyte proliferation assays to HPV and HIV antigens
 - cytokine induction and profile
 - activation and proportional representation of lymphocyte subset populations (HIV-infected patients only)
- Cross-sectional and longitudinal characterization of HPV and HIV knowledge and risk and sexual behaviors in the study cohort populations.

Specific statistical approaches to the primary immunogenicity and virologic safety analyses, and secondary analyses of HIV-related parameters (use of HAART, CD4 cell count and HIV-1 RNA levels) on vaccine immunogenicity are outlined in complete detail in the statistical section 5.4.

5.3 TOXICITY CRITERIA

This study will utilize NCI Common Terminology Criteria for Adverse Events (CTCAE) version 3.0, published June 10, 2003, for toxicity and adverse event monitoring and reporting. (Refer to: http://ctep.info.nih.gov/reporting/ctc_v30.html). All clinical treatment areas will have access to a copy of CTCAE version 3.0.

6 STATISTICAL SECTION

Primary analyses will be for immunogenicity: fold increase in HPV titer following vaccination and for safety.

6.1 PRIMARY IMMUNOGENICITY ANALYSIS PART I

Does vaccine-induced antibody titer differ between study cohorts at a pre-determined primary timepoint X?

4 comparisons:

- Cohort 1 (HIV-infected, on HAART) vs. cohort 2 (HIV-infected, no HAART)
- Cohort 1 (HIV-infected, on HAART) vs. cohort 3 (healthy, HIV negative controls)
- Cohort 2 (HIV-infected, no HAART) vs. cohort 3 (healthy, HIV negative controls)
- Cohorts 1 & 2 (HIV-infected) vs. cohort 3 (healthy, HIV negative controls)

For each pairwise comparison, allowing for 4 primary comparisons as defined above among cohorts at a single time-point, we will need to plan to test with as small as a 0.0125 p value for each of the 4 comparisons in the primary analysis. With 35 vaccine recipients in each of Cohorts 1, 2 and 3, there will be at least 94% power to detect differences among cohorts as described above, of 1.0 standard deviation effect size for a single time-point.

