6.2 PRIMARY IMMUNOGENICITY ANALYSIS PART II

What is the change in vaccine induced antibody titer between baseline and timepoint X?

Timepoints for Analysis:

- Timepoint 1 Baseline vs. Month 7 (1mos s/p 3 vaccinations)
- Timepoint 2 Baseline vs. Month 12 (6mos s/p 3 vaccinations)
- Timepoint 3 Baseline vs. Month 24 (18mos s/p 3 vaccinations)
- Timepoint 4 Baseline vs. Month 48 (42mos s/p 3 vaccinations)

Comparisons between baseline and each of the 4 time-points noted above will be made for each of the three defined cohorts of patients receiving vaccine. As there will be 12 paired comparisons performed, the individual tests will be performed using a 0.004 alpha level to adjust for multiple comparisons ($0.05/(3 \times 4) = 0.0042$, which rounds to 0.004). With 35 patients in each of Cohorts 1, 2 and 3 there will be 90% power to detect a change with an effect size equal to 0.75 SD from baseline to each time-point using a 0.004 alpha level two-tailed test, and 99% power to detect a change with a 1 SD effect size from baseline, again using a 0.004 alpha level two-tailed test.

In addition, based upon a 0.003 alpha level two-tailed test, and 1 SD effect size with 4 comparisons between cohorts at N = 4 primary time-points as outlined above, 35 patients receiving vaccine in each of cohorts 1, 2, and 3 will have the following characteristics for the comparisons: Cohorts 1 and 2, or 1 and 3, or 2 and 3 can each be compared with 85% power. In addition, the comparison of Cohorts 1 and 2 vs. 3 will have 96% power with the combined total of 70 patients vs. 35 patients in Cohort 3. The stringent 0.003 alpha level was selected to adjust according to Bonferroni principles: $0.05/(4 \text{ comparisons} \times 4 \text{ time-points}) = 0.05/16 = 0.0031$, or about 0.003).

Finally, in addition to comparisons at each time point, a linear mixed model approach may be used to perform an evaluation of the longitudinal patterns of change. This analysis may also be able to account

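### The same four cohort contrasts are primary at 0.0125 at an unnamed visit (6.1) and at 0.003 at four visits (6.2), and no rule says which level governs

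*Combined protocol and SAP*

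**What the plan says.** Section 6.1 (Primary Immunogenicity Analysis Part I) poses the question "Does vaccine-induced antibody titer differ between study cohorts at a pre-determined primary timepoint X". It lists four contrasts: cohort 1 v 2, 1 v 3, 2 v 3, and 1 and 2 pooled v 3. The level is set by "allowing for 4 primary comparisons as defined above among cohorts at a single time-point", so that "we will need to plan to test with as small as a 0.0125 p value for each of the 4 comparisons". The stated power is "there will be at least 94% power to detect differences among cohorts as described above, of 1.0 standard deviation effect size for a single time-point". The section does not say which visit X is.

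Section 6.2 (Part II) opens with change from baseline within each cohort at months 7, 12, 24 and 48, using 12 paired tests at 0.004. It then returns to the cohort contrasts, "based upon a 0.003 alpha level two-tailed test, and 1 SD effect size with 4 comparisons between cohorts at N = 4 primary time-points". It gives 85% power for each pairwise contrast and 96% for the pooled one (70 v 35), and explains: "The stringent 0.003 alpha level was selected to adjust according to Bonferroni principles", with the divisor 16 (4 contrasts by 4 visits).

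The end of 6.2 calls both parts primary. It also removes, type by type, subjects who are seropositive at baseline. Section 1.1 lists the cohort comparisons among the secondary objectives.

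**The concern.** If X is one of the four months in 6.2, the contrasts at X are judged twice, each time as a primary analysis and at different levels. A result between the two levels would be a positive primary finding under 6.1 and a negative one under 6.2, and the plan offers no hierarchy or gatekeeping to settle it. Because X is described as fixed in advance but is not written down, a reader of the eventual report also could not confirm that the looser level was attached to its visit before the titers were known.

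**Working it through.** **Inputs.** 35 per cohort, 1 SD effect, four contrasts, levels 0.0125 and 0.003, four visits (6.1 and 6.2). 6.2 is two-sided. 6.1 does not state sidedness; two-sided fits its figure best.

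**1. The plan's own figures.** The levels are 0.05/4 = 0.0125 and 0.05/16 = 0.003125, rounded to 0.003. Power is taken from the non-central t with noncentrality d/√(1/n₁ + 1/n₂) and n₁ + n₂ − 2 degrees of freedom. For d = 1 and 35 v 35, the noncentrality is 1/√(2/35) = 4.18.

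| Contrast | Level | Stated | Recomputed |
|---|---|---|---|
| 35 v 35 | 0.0125 | at least 94% | 94.4% |
| 35 v 35 | 0.003 | 85% | 86.0% |
| 70 v 35 | 0.003 | 96% | 96.1% |

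The arithmetic is sound. The fault lies in the testing structure.

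**2. Can X be one of the four months?** Sections 3.5.2 and 3.5.3 and Appendices 2 and 3 schedule the Merck titer assay after vaccination only at months 7, 12, 24 and 48. On that schedule the answer is yes, and the overlap is certain. Other places differ: 5.2 describes titers after each dose and every 6 months, 6.5 includes months 1, 3 and 36, and Appendix 6 lists 13 months for the Merck assay. If X were one of those extra months there would be no overlap, but X would still be unnamed.

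**3. Size of the conflict zone.** For 35 v 35 the critical t values on 68 degrees of freedom are 2.566 (0.0125) and 3.078 (0.003). Multiplying by √(2/35) gives observed differences of 0.61 and 0.74 SD. Results between these pass 6.1 and fail 6.2. The chance of landing there is power at 0.0125 minus power at 0.003:

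| Contrast | True difference | Power at 0.0125 | Power at 0.003 | Conflict |
|---|---|---|---|---|
| 35 v 35 | 0.5 SD | 32.5% | 17.3% | 15.2% |
| 35 v 35 | 0.7 SD | 64.2% | 44.7% | 19.5% |
| 35 v 35 | 1 SD | 94.4% | 86.0% | 8.4% |
| 70 v 35 | 1 SD | 98.8% | 96.1% | 2.7% |

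**4. Error rate for the cohort contrasts, one HPV type.** Bonferroni bounds:
- 6.1 alone: 4 × 0.0125 = 0.050.
- 6.2 alone: 16 × 0.003 = 0.048.
- Both, X fixed in advance: 4 × 0.0125 + 12 × 0.003 = 0.086.
- X chosen after seeing titers: 16 × 0.0125 = 0.20.

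Bounds overstate the error when tests are correlated, so the null was also simulated (60,000 trials per setting, three cohorts of 35, four visits, equal correlation between visits). The documents give no between-visit correlation, so these values are assumptions:

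| Correlation | Both families, X fixed | X chosen afterwards |
|---|---|---|
| 0 | 6.3% | 13.6% |
| 0.5 | 5.6% | 11.7% |
| 0.7 | 5.2% | 10.3% |
| 0.9 | 4.1% | 7.3% |

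The four tests of 6.1 at a fixed visit, taken alone, gave 3.5% to 3.7%.

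**The case against.** The strongest reply is that the plan does control error. Each Bonferroni family holds 5% by itself, and 6.1 says X is settled beforehand. Taken at its word, the double rule costs about one percentage point, or nothing at high correlation. This stands. A reader might infer from the two levels that the 5% error rate is not held. The documents do not support that as a flat statement, because the 7-12% figures need X to be picked after the titers are seen, which is contrary to the text. What remains is that the choice of X cannot be verified.

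A second reply is that X need not be one of the four months, given 5.2, 6.5 and Appendix 6. This is also fair: the overlap follows from the body-text schedule and Appendices 2 and 3, and not from every section.

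A third is that 6.1 concerns titer at X, whereas the cohort contrasts in 6.2 sit under a question about change from baseline, so the two p-values may not be identical. With baseline seropositives removed type by type, and with section 6 defining immunogenicity as fold increase, the two are close. The plan does not separate them as different endpoints.

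Finally, the wording of 6.1 ("we will need to plan to test with as small as a 0.0125 p value for each of the 4 comparisons in the primary analysis") could hint at a step-down procedure. None is specified, and it would not say which section prevails. Nor does X follow by implication: 6.3 marks its lead time-point as primary, and the list in 6.2 carries no such mark.

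**Conclusion.** The concern holds as a conflict between two stated primary rules. The plan can return opposite primary verdicts on one cohort contrast, and it has no means of choosing between them. At the plan's own 1 SD effect the chance is modest (8% pairwise, 2.7% for 70 v 35). At smaller true differences the pairwise chance is larger (15% at 0.5 SD, 19.5% at 0.7 SD). These figures assume two-sided t-tests, full cohorts of 35, an X among months 7, 12, 24 and 48, and essentially the same titer measure in both sections.

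The effect on error is secondary: about 4-6% with X fixed in advance, and about 7-12% if it were chosen afterwards (assumed correlation 0.9 to 0.5). Nothing in the documents shows that X was or will be chosen that way. The point deserves correction, and a change of wording is enough.

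**What to change.** Use one primary rule for the cohort contrasts. Either of these works:

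- **(a) One visit.** Name X, and make the four contrasts there at 0.0125 the only primary cohort tests. Label months 12, 24 and 48 secondary. Month 7 is the natural choice: 1.2.5 reports that titers peaked then, and it is first in the 6.2 list. The 1.2.5 titer results come from girls and women, and the same section says the vaccine had not been given to people with HIV. Bound 0.05; power 94.4% pairwise and 98.8% for 70 v 35.
- **(b) Four visits.** Keep all 16 tests primary at 0.003, and delete the 0.0125 rule and its 94% power figure. Bound 0.048; power 86.0% pairwise and 96.1% for 70 v 35.

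Neither needs more patients, visits or assays. Option (a) takes the primary label from the durability visits, although 5.2 puts duration within the study's focus. Option (b) lowers the stated pairwise power.

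With either option, state that the 5% applies per HPV type and to the cohort contrasts only. The 12 within-cohort tests at 0.004 add a further 12 × 0.004 = 0.048 to any bound, and neither level adjusts for the four HPV types. Reconcile the primary label with section 1.1, and the titer months in 5.2, 6.5 and Appendix 6 with the schedule. If titers have already been analysed, cite a dated record of X or report the choice as post hoc.

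### Sections 6.1 and 6.2 divide alpha by four for contrasts among only three cohort means: valid, but more conservative than 5% family-wise control requires

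*Combined protocol and SAP*

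**What the plan says.** Section 6.1 lists four comparisons of antibody titer at one primary time-point: Cohort 1 v 2, 1 v 3, 2 v 3, and Cohorts 1 and 2 together v 3. It plans to "test with as small as a 0.0125 p value for each of the 4 comparisons in the primary analysis". On power it says: "With 35 vaccine recipients in each of Cohorts 1, 2 and 3, there will be at least 94% power to detect differences among cohorts", for a difference "of 1.0 standard deviation effect size for a single time-point".

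Section 6.2 takes the same four contrasts to four time-points, "based upon a 0.003 alpha level two-tailed test, and 1 SD effect size with 4 comparisons between cohorts at N = 4 primary time-points". It explains: "The stringent 0.003 alpha level was selected to adjust according to Bonferroni principles", the divisor being 4 comparisons x 4 time-points = 16. Its powers are "Cohorts 1 and 2, or 1 and 3, or 2 and 3 can each be compared with 85% power" and "the comparison of Cohorts 1 and 2 vs. 3 will have 96% power with the combined total of 70 patients vs. 35 patients".

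Section 6.2 also has 12 within-cohort paired tests at 0.004, which are a separate family. Its closing paragraph shows that the analysis is run by HPV type, with baseline-seropositive subjects left out for that type. Neither section names an overall three-cohort test, a gatekeeping order or a step-down procedure, and neither divides alpha over the four HPV types.

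**The concern.** Bonferroni treats the four contrasts as if any number of their null hypotheses could be true together. With three means there are only two degrees of freedom between cohorts, and that restricts which nulls can hold at once. A procedure that uses the restriction can test each contrast at a larger alpha with the same family-wise guarantee.

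What is at stake is power for the cohort comparisons at a fixed 35 per cohort, above all for differences below 1 SD. These comparisons include HAART v no HAART, which Section 1.1 lists as an objective.

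**Working it through.** **Inputs.** From 6.1: four contrasts, 35 per cohort, 1.0 SD, alpha 0.0125. From 6.2: alpha 0.003 two-tailed, 1 SD, 70 v 35 for the pooled contrast. Assumptions: 6.1 is also two-sided (it does not say), data are normal on the analysis scale, and SDs are equal unless stated otherwise.

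**Step 1: the plan's own figures.** Two-sample t-test, noncentrality = d / sqrt(1/n1 + 1/n2).
- Pairwise: 1 / sqrt(2/35) = 4.18, 68 df. Pooled: 1 / sqrt(1/70 + 1/35) = 4.83, 103 df.
- 6.1 pairwise, alpha 0.0125 (critical t 2.57): 94.4%, stated as at least 94%.
- 6.1 pooled: 98.8%.
- 6.2 pairwise, alpha 0.003 (critical t 3.08): 86.0%, stated 85%. At 0.05/16 = 0.003125 it is 86.3%.
- 6.2 pooled: 96.1%, stated 96%.

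The stated powers reproduce.

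**Step 2: which nulls can be true together.** Write the means as m1, m2, m3.
- Any two of m1=m2, m1=m3 and m2=m3 give the third.
- If the pooled null holds (a weighted average of m1 and m2 equals m3) and m1=m2, then both equal m3.
- If the pooled null holds and m1=m3, then m2=m3. By symmetry m2=m3 gives m1=m3.

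So either no null is true, exactly one is, or all three means are equal. In a closed test every intersection of two or more nulls is the single hypothesis m1=m2=m3. Test that at 0.05. If it is rejected, at most one null is true, and each contrast can be tested at 0.05 with strong control.

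**Step 3: simulated family-wise error** (35 per cohort, equal SDs, F gate at 0.05, 400,000 trials per scenario).

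| True state | Gate | Bonferroni |
|---|---|---|
| All means equal | 4.97% | 3.6% |
| One cohort far from the other two | 5.0% | 1.2% |

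Across partial nulls the gate stayed at or below about 5.1%, which is within simulation error of 5%.

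**Step 4: simulated power, 6.1** (F gate and contrasts at 0.05).

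| Contrast | Bonferroni | Gated |
|---|---|---|
| Pairwise 1.0 SD, third cohort equal to one of the two | 94.4% | 98.2% |
| Pairwise 1.0 SD, third cohort midway | 94.4% | 96.6% |
| Pooled 1.0 SD | 98.8% | 99.3% |
| HIV cohort v control 0.75 SD, both HIV cohorts shifted | 71% | 84% |
| Same, 0.5 SD | 33% | 46% |
| Pooled 0.5 SD | 45.3% | 53.9% |

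**Step 5: 6.2.** The gate removes the factor for contrasts but not the factor for time-points. A gate at 0.05 at each of four time-points could reach 1 - 0.95^4 = 18.5% if they were independent. The level is therefore 0.05/4 = 0.0125 for both gate and contrasts, in place of 0.05/16. At 1.0 SD, pairwise power goes from 86.3% to 89.7% (third cohort midway) or 93.7% (third equal to one of the two). Pooled power goes from 96.2% to 97.0%.

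**Step 6: unequal SDs and cohort sizes.** The type-specific exclusions in 6.2 can make cohort sizes unequal, and the documents give no SDs. With assumed sizes 35/22/33 and SDs 1/1.5/1, the classical F gate has a global-null error of about 7.3-7.5% against 4.8% for Bonferroni. A Welch gate with Welch contrasts gives 4.9-5.0%.

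**Step 7: a step-down without a gate.** By Step 2, Shaffer's method tests the smallest p-value at 0.0125 and, if that is rejected, the rest at 0.05. With both HIV cohorts shifted, pairwise power in 6.1 is 98.1% at 1.0 SD, 83.3% at 0.75 SD and 44.0% at 0.5 SD, 0 to 2 points below the gate. It gains less when the third cohort lies midway: a further run of 200,000 trials gave 94.8-95.3% at 1.0 SD.

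**The case against.** The strongest reply is that nothing is wrong. Bonferroni is valid, its levels are disclosed, and its powers are right. That stands: this is an efficiency improvement.

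A second reply is that the gain is small where the plan set its target. That also stands for full cohorts at 1.0 SD: about 2-4 points pairwise in 6.1, 3-7 in 6.2, and under 1 point pooled. The chance of declaring at least one cohort difference in 6.1 barely moves, from 99.1% to 99.3% when one cohort differs by 1 SD and from 52.1% to 55.8% when it differs by 0.5 SD. A reader might infer that the plan loses a great deal of power or is underpowered. The documents do not support that at the effect size they chose.

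Third, the words "as small as" in 6.1 could be read as the first step of a step-down method, which would already capture much of the gain. The wording allows this but names no such method, and 6.2 fixes 0.003.

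Fourth, the unused alpha has some value. It partly offsets the lack of adjustment over four HPV types. If the types were independent (a worst-case assumption), the error across them would be 1 - (1 - 0.05)^4 = 18.5% with the gate against 1 - (1 - 0.036)^4 = 13.6% with Bonferroni. A reader might infer that the closed procedure protects the whole trial at 5%. It does so only per type, as the plan does now. Bonferroni also brings matching simultaneous confidence intervals. Both points stand as costs.

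The objection about unequal SDs defeats a classical F gate but not a Welch one.

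**Conclusion.** The point holds as a low-cost improvement. The division by four exceeds what strong 5% control of these contrasts needs, and a closed procedure raises pairwise power modestly at 1.0 SD and more for smaller differences (13 points at both 0.75 and 0.5 SD in 6.1, with both HIV cohorts shifted). The logical step in Step 2 is exact. The power figures assume 35 evaluable subjects per cohort, normal data and equal SDs.

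Two limits apply. The 6.2 contrasts may move from 0.003 to 0.0125, not to 0.05. The 12 paired tests are a separate family that a three-cohort gate does not address.

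**What to change.** - **6.1:** on the log-titer scale, test the three cohorts with a Welch one-way ANOVA at 0.05. If significant, test each of the four contrasts at 0.05 with Welch t-tests. A Shaffer step-down on Welch p-values (smallest at 0.0125, then the rest at 0.05) rests on the same argument and needs no gate, with slightly less power.
- **6.2 cohort contrasts:** at each of the four time-points, gate at 0.0125 and then test the contrasts at 0.0125 in place of 0.003.
- **6.2 paired tests:** leave the 12 tests at 0.004 unchanged.
- **Both sections:** restate the powers, and say that the 5% applies per HPV type.

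The change is SAP wording only and needs no new data or patients. It should be fixed before titers are compared between cohorts. The costs are the loss of matching Bonferroni simultaneous intervals, so the plan should say which intervals will be reported, and less spare alpha against testing four HPV types.

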6.2 PRIMARY IMMUNOGENICITY ANALYSIS PART II

What is the change in vaccine induced antibody titer between baseline and timepoint X?

Timepoints for Analysis:

- Timepoint 1 Baseline vs. Month 7 (1mos s/p 3 vaccinations)
- Timepoint 2 Baseline vs. Month 12 (6mos s/p 3 vaccinations)
- Timepoint 3 Baseline vs. Month 24 (18mos s/p 3 vaccinations)
- Timepoint 4 Baseline vs. Month 48 (42mos s/p 3 vaccinations)

Comparisons between baseline and each of the 4 time-points noted above will be made for each of the three defined cohorts of patients receiving vaccine. As there will be 12 paired comparisons performed, the individual tests will be performed using a 0.004 alpha level to adjust for multiple comparisons ($0.05/(3 \times 4) = 0.0042$, which rounds to 0.004). With 35 patients in each of Cohorts 1, 2 and 3 there will be 90% power to detect a change with an effect size equal to 0.75 SD from baseline to each time-point using a 0.004 alpha level two-tailed test, and 99% power to detect a change with a 1 SD effect size from baseline, again using a 0.004 alpha level two-tailed test.

In addition, based upon a 0.003 alpha level two-tailed test, and 1 SD effect size with 4 comparisons between cohorts at N = 4 primary time-points as outlined above, 35 patients receiving vaccine in each of cohorts 1, 2, and 3 will have the following characteristics for the comparisons: Cohorts 1 and 2, or 1 and 3, or 2 and 3 can each be compared with 85% power. In addition, the comparison of Cohorts 1 and 2 vs. 3 will have 96% power with the combined total of 70 patients vs. 35 patients in Cohort 3. The stringent 0.003 alpha level was selected to adjust according to Bonferroni principles: $0.05/(4 \text{ comparisons} \times 4 \text{ time-points}) = 0.05/16 = 0.0031$, or about 0.003).

Finally, in addition to comparisons at each time point, a linear mixed model approach may be used to perform an evaluation of the longitudinal patterns of change. This analysis may also be able to account

for any patients who are unable to be included at each time point, should that be necessary. For both part I and part II primary immunogenicity analyses, seropositivity at baseline for one of the HPV vaccine types will exclude the subject from inclusion in the analysis for that HPV type. If initial cross-sectional evaluation of HPV serostatus among study subjects within each cohort reveals a significant number of subjects with baseline seropositivity to one or more vaccine HPV types resulting in their exclusion from the immunogenicity analysis, expanded enrollment within a cohort may be necessary to ensure the validity of the statistical analyses that have been proposed.

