3.7 OFF TREATMENT AND OFF STUDY CRITERIA

- Off Treatment- Any Grade III or higher toxicity possibly or probably related to vaccine that does not resolve to baseline within 4 weeks with appropriate intervention.
- Off Treatment- Any Grade IV toxicity unrelated to vaccine that does not resolve to within grade 1 or lower within 8 wks.
- Off Treatment- Severe or life-threatening immediate hypersensitivity reactions following receipt of quadrivalent HPV vaccine.
- Off Treatment and Off Study- Development of an acute life-threatening condition or cancer.
- Off Treatment and Off Study- Inability to adhere to HAART.
- Off Treatment and Off Study- Discontinuation of HAART for >6 wks due to antiretroviral toxicity.
- Off Treatment- > 30% decrease in baseline CD4 cell count or percent or decrease in absolute CD4 count to < 350 cells/mm³ confirmed by at least 2 measurements 4 weeks apart.
- Off Treatment- Increase in HIV-1 RNA levels to > 100,000 copies/ml confirmed by at least 2 measurements 4 weeks apart.
- Off Treatment- Pregnancy. Patients will be taken off-study and advised to defer completion of their vaccination regimen until resolution of the pregnancy. Patients will also be reported to the Merck Pregnancy Registry [contact]) that monitors fetal outcomes of pregnant women exposed to GARDASIL®.
- Off Study- Non-compliance with study protocol evaluations and visits.
- Off Study- Study discontinuation at the request of the patient or at the discretion of the Principal Investigator or Lead Associate Investigator if they determine that study withdrawal is in the patient's best interest.

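### Section 6.2 commits only to separate titer comparisons at each visit and leaves the mixed model optional; a firm repeated-measures model would recover power at months 12 to 48 and protect against unequal, titer-linked loss.

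*Combined protocol and SAP*

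**What the plan says.** Section 6.2 lists four primary time-points, months 7, 12, 24 and 48, and two sets of tests.

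- Within each cohort, each time-point is compared with baseline: 12 paired tests, with "90% power to detect a change with an effect size equal to 0.75 SD from baseline to each time-point using a 0.004 alpha level two-tailed".
- Between cohorts, the power statement is "based upon a 0.003 alpha level two-tailed test, and 1 SD effect size with 4 comparisons between cohorts at N = 4 primary time-points". It gives that "Cohorts 1 and 2, or 1 and 3, or 2 and 3 can each be compared with 85% power", and that the pooled HIV cohorts against controls "will have 96% power with the combined total of 70 patients vs. 35 patients in Cohort 3".

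Both power statements count all 35 subjects per cohort at every time-point.

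The mixed model comes last: "in addition to comparisons at each time point, a linear mixed model approach may be used to perform an evaluation" of the longitudinal pattern. The section adds that this model might account "for any patients who are unable to be included at each time point, should that be necessary". That is the only text on missing titers. There is no missingness assumption, imputation rule or sensitivity analysis.

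Three other places bear on loss.

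- Section 3.7 takes subjects off study for several reasons, including "Off Treatment and Off Study- Inability to adhere to HAART" and stopping HAART for more than 6 weeks because of toxicity.
- Section 3.3.1 allows up to 10 replacements in each HIV cohort, but only for an antiretroviral change or start before month 7.
- Section 3.8.3 makes the titer sample at early exit optional.

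**The concern.** Follow-up lasts 48 months, and the late visits address how long the response lasts. A subject who leaves after month 7 has a month 7 titer that carries information about the later ones. A separate test at month 24 or 48 does not use it.

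Two things follow. First, precision is lost even if leaving has nothing to do with titer. Second, if leaving is related to titer and differs between cohorts, the remaining subjects no longer represent their cohort in the same way. If low responders leave an HIV cohort more often than they leave the control cohort, the late HIV-versus-control deficit is understated.

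Unequal loss is plausible. The two HAART off-study rules cannot apply to the HIV-negative Cohort 3. They mainly concern Cohort 1, and reach Cohort 2 only once a subject has started therapy. Loss after month 7 is not replaced. Because the model is optional, the method could also be chosen after the pattern of loss is known.

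**Working it through.** **1. The plan's own figures reproduce.** Use the noncentral t distribution. Between cohorts, df = n1 + n2 − 2 and noncentrality = d / √(1/n1 + 1/n2). For paired tests, df = n − 1 and noncentrality = d√n.

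- 35 v 35, d = 1, alpha 0.003: noncentrality √17.5 = 4.18, power 86.0% (stated 85%).
- 70 v 35, same alpha: noncentrality √23.3 = 4.83, power 96.1% (stated 96%).
- Paired, 0.75 SD, alpha 0.004: noncentrality 0.75√35 = 4.44, power 90.1% (stated 90%). At 1 SD, 99.6% (stated 99%).
- Section 6.1, 35 v 35, alpha 0.0125: 94.4% (stated as "at least 94% power to detect differences among cohorts as described above, of 1.0 standard deviation effect size for a single time-point").

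The arithmetic is right for complete data. It makes no allowance for loss.

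**2. Power of the per-visit tests if the same share is lost in every cohort (assumed shares).**

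| Loss | Left per cohort | Pairwise, 0.003 | Pooled v Cohort 3, 0.003 | Paired 0.75 SD, 0.004 |
|---|---|---|---|---|
| 10% | 32 | 81% | 94% | 86% |
| 20% | 28 | 73% | 89% | 78% |
| 30% | 24 | 63% | 82% | 68% |
| 40% | 21 | 54% | 74% | 58% |

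**3. What the earlier titers recover under random loss.** Let f be the fraction still sampled and ρ the month 7 to month 48 correlation. The variance of a cohort's month 48 mean is σ²/(nf) per visit. In large samples it is (σ²/n)[ρ² + (1 − ρ²)/f] for a likelihood analysis that also uses month 7. With n = 35 and f = 0.7:

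- per visit: effective n = 35 × 0.7 = 24.5;
- ρ = 0.6: 0.36 + 0.64/0.7 = 1.274, effective n = 35/1.274 = 27.5;
- ρ = 0.8: 0.64 + 0.36/0.7 = 1.154, effective n = 35/1.154 = 30.3.

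**4. Bias under titer-linked loss.** Suppose the log-odds of leaving rise by 1 per SD of lower month 7 titer. The mean month 7 titer of those who stay then lies above the cohort mean by E[z·s(z)]/E[s(z)], where z is the standardised titer and s(z) the logistic probability of staying. Numerically this is 0.253 SD at 30% loss, 0.133 at 15% and 0.091 at 10%. The month 48 shift is ρ times this, so with ρ = 0.6 to 0.8:

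- linked in both cohorts, 30% v 10%: ρ × (0.253 − 0.091) = 0.10 to 0.13 SD;
- linked in both, 30% v 15%: ρ × (0.253 − 0.133) = 0.07 to 0.10 SD;
- linked in the 30% cohort only, 15% random loss in the other: ρ × 0.253 = 0.15 to 0.20 SD;
- equal loss, same mechanism: ρ × (0.253 − 0.253) = 0.

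**5. Simulation of the month 48 contrast.** Inputs: 35 per cohort, true difference 1 SD, ρ = 0.6 to 0.8, two-sided alpha 0.003. A t-test on those sampled is compared with a likelihood analysis using month 7.

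| Loss | Per-visit estimate | Per-visit power | Likelihood estimate | Likelihood power |
|---|---|---|---|---|
| Random, 30% in both | 1.00 SD | 63–65% | 1.00 SD | 70–76% |
| Linked in both, 30% v 10–15% | 0.87–0.93 SD | about 59–64% | 1.00 SD | 75–80% |
| Linked in one only, 30% v 15% random | 0.80–0.85 SD | 45–52% | 1.00 SD | 74–80% |

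With no true difference, the last row gives a per-visit type I error of about 0.7–1.4% against the nominal 0.3%. A separate four-visit simulation agrees. At 30% v 10% linked loss the per-visit bias was 0.10 to 0.12 SD, and at 40% v 10% it was 0.14 to 0.20 SD. The bias of the likelihood estimate was about 0.01 SD.

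**The case against.** Several objections have force.

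- **No named available-case rule.** The documents name neither that rule nor a t-test for titers. Both are inferred, although Section 6.2 itself foresees subjects who cannot be included at a time point, and its powers match t-tests.
- **The sponsor already names the model.** The gap is between an option and a commitment, in a non-randomized phase I study.
- **Little ties leaving to titer.** Pregnancy and non-compliance apply to all three cohorts. In Section 3.7 the CD4 and HIV-1 RNA rules are labelled off treatment, not off study; Section 6.7 describes such subjects as removed from the study, and the two passages must be reconciled. Section 3.3.1 keeps subjects on study when therapy is changed or started after month 7. No section links leaving the study to HPV titer.
- **The model is not a cure-all.** In steps 4 and 5 linked loss depends only on the observed month 7 titer, which favours the model. When loss was made to depend on the month 48 value itself, the likelihood estimate was also biased: 0.86 SD, against 0.74 SD for the t-test.

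A reader might infer that the late contrasts are biased as planned, or that the month 7 titers go unused. The documents support neither. Bias in the contrast needs loss that is related to titer and differs between cohorts, and no section gives its size. The month 7 titers are used in the month 7 comparison; they are ignored only in the later ones. The precision argument survives all of these objections, because it holds under random loss.

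**Conclusion.** The point holds as a cheap and worthwhile improvement, not as a demonstrated bias. Section 6.2 commits to the less efficient method for its late primary comparisons and leaves the better one optional. At an assumed 30% random loss, the per-visit approach gives up roughly 5 to 13 points of month 48 power (63–65% against 70–76%) with no bias in either method. If loss is linked to low titer and unequal, the late difference is also understated: by about 0.07 to 0.13 SD when the mechanism is common to both cohorts, and by about 0.15 to 0.20 SD in the near-worst case of linkage in one cohort only. Equal loss by the same mechanism leaves the contrast unbiased.

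All of these sizes rest on assumed loss rates, an assumed correlation of 0.6 to 0.8 and a 1 SD true difference. A reader might take the stated 85%, 90% and 96% powers to be wrong. They are arithmetically correct for complete data and lack only an allowance for loss.

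**What to change.** In Section 6.2, replace the optional wording with a firm primary method.

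- For each HPV type, fit one mixed model for repeated measures to log10 titer at months 7, 12, 24 and 48. Use cohort, categorical visit, cohort-by-visit, unstructured covariance and a small-sample degrees-of-freedom correction.
- Include every subject seronegative for that type at baseline who has at least one of these post-vaccination titers.
- Take the four cohort contrasts at each visit from this model at the stated 0.003 level, and state how Cohorts 1 and 2 are weighted in the pooled contrast.
- Obtain the 12 within-cohort changes from baseline, at 0.004, from the same framework, or state that they remain paired tests.
- State the missing-at-random assumption, keep the per-visit tests as supportive, and add a sensitivity analysis for loss that depends on unobserved titers, for example a delta adjustment.

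The cost is revised analysis wording and somewhat more analysis work, with no new samples or subjects. The price is reliance on missing at random given the observed titers. That is a weaker assumption than the per-visit tests need in general, but it cannot be verified, hence the sensitivity analysis.
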